9.6 Efficacy Endpoint Assessments

9.6.1 General Considerations

A Bayesian adaptive design is adopted to address the following objectives:

1. Demonstrate superiority of the pooled middle and high doses over placebo in the ovulation rate
2. Evaluate the dose-response relationship

The adaptive design includes two interim analyses, conducted after approximately 9 and 12 patients per arm enrolling in the study, respectively. The interim analysis provides an opportunity for stopping the trial early due to efficacy success utilizing the group sequential strategy or due to efficacy futility through Bayesian predictive probability of success. Furthermore, it allows the low dose to be dropped following the interim look if it shows a much lower response rate compared with the middle and high doses.

Each interim analysis will result in one of the following possible outcomes:

1. Continue the trial with all arms
2. Continue the trial without the low dose
3. Declare early success, but continue the trial without placebo
4. Declare early success and stop the trial (both placebo and low dose dropped)
5. Stop the trial for futility

When the primary efficacy analysis is not successful at the interim analysis, and if the ovulation rate in the low-dose arm is sufficiently low, satisfying

$$R_{\text{low}} < (R_{\text{high}+\text{middle}}) - 0.2, \quad (1)$$

then the trial will continue without the low dose, resulting in outcome #2 listed above. Note that R_{low} and $R_{\text{high}+\text{middle}}$ in inequality (1) are the observed ovulation rates in the low dose arm and the combined middle- and high-dose arms, respectively. However, if inequality (1) is not satisfied, then the trial will continue with all arms (outcome #1 listed above).

Conversely, when success on the primary efficacy analysis is declared at an interim analysis, if the response rate in the low-dose arm meets the condition in inequality (1), then the trial is completed at this point (outcome #4 listed above) with dose selection performed using the ED80 rule (see below).

In the case the primary efficacy analysis is successful, but the response rate in the low-dose arm is within 20% from the combined low- and high-dose success rate, the trial is not stopped immediately. Rather, the trial will continue to enroll additional patients into the low-, middle- and high-dose arms to further assess dose responses.

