9.9 Interim Analyses

Two interim analyses are planned after approximately 9 and 12 patients per arm complete the study. The details of the interim analysis strategy are described in Section 9.6 and SAP.

An independent data monitoring committee consisting of two unblinded clinicians and one unblinded statistician will be set up to review the interim analysis study results and make recommendations for the direction of the study, in accordance with the adaptive design decision-making rules specified in Section 9.6. In addition, an independent statistician and programmer will be identified to generate the data analysis output. Individuals involved in the first and second interim analysis of the study will not be involved in the conduct of the study afterwards; individual patient identification will not be released to anyone who is directly involved in the conduct of the study.

The interim analysis process, the measures used to protect the blind and the integrity of the study, the communication plan, and the confidentiality agreement will be described in a separate document.

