8.1.2 Treatment Compliance

Summary (descriptive) statistics will be presented for the number of OmniPods applied by each patient and the treatment compliance during the patient's actual treatment period, defined as the actual days of treatment exposure divided by the patient's total treatment exposure duration. The actual days of treatment exposure is the sum of the durations of individual applications. For each OmniPod application, the duration is calculated as: date of next application — date of current application, or 3, whichever is smaller. For the last application, it is equal to 3.

.

9 Efficacy

A Bayesian adaptive design is adopted to address the following objectives:

- 1. Demonstrate superiority of the pooled middle and high doses over placebo
- 2. Evaluate the dose-response relationship

The adaptive design includes two interim analyses, conducted after approximately 9 and 12 patients per arm enrolling in the study, respectively. Each interim analysis provides opportunities for stopping the trial early due to efficacy success utilizing the group sequential strategy or due to efficacy futility through Bayesian predictive probability of success. Furthermore, it allows the low dose to be dropped following the interim look if it shows a much lower response rate compared with the middle and high doses.

Each interim analysis will result in one of the following outcomes:

- 1. Continue the trial with all arms
- 2. Continue the trial without the low dose
- 3. Declare early success, but continue the trial without placebo
- 4. Declare early success and stop the trial (both placebo and low dose dropped)
- 5. Stop the trial for futility

When the primary efficacy analysis is not successful at the interim analysis, and if the ovulation rate in the low-dose arm is sufficiently low, satisfying

$$R_{low} \le (R_{high+middle}) - 0.2, \tag{1}$$

then the trial will continue without the low dose, resulting in outcome #2 above. Note that R_{low} and $R_{high+middle}$ in the inequality (1) above are the observed ovulation rates in the low dose arm and the combined middle- and high-dose arms, respectively. However, if inequality (1) is not satisfied, then the trial will continue with all arms (outcome #1).

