Conversely, when success on the primary efficacy analysis is declared at an interim analysis, if the response rate in the low-dose arm meets the condition in inequality (1), then the trial is completed at this point (outcome #4) with dose selection performed using the ED80 rule (see below).

In the case the primary efficacy analysis is successful, but the response rate in the low-dose arm is within 20% from the combined low- and high-dose success rate, the trial is not stopped immediately. Rather, the trial will continue to enroll additional patients into the low-, middle- and high-dose arms to further assess dose responses (outcome #3).

Finally, the trial may terminate (outcome #5) as a result of a low predictive probability of success (<0.05) given the data collected at the interim analysis.

At the end of the study, for a trial that achieves efficacy success, the dose to be selected is the ED80 dose, defined as the lowest dose that retains at least 80% of the largest treatment effect, i.e.

$$(R_{ED80} - R_{placebo}) \ge (R_{maximum} - R_{placebo}) \times 0.8, \tag{2}$$

where $R_{maximum}$ is the observed ovulation rate in the most effective dose arm, $R_{placebo}$ is the observed ovulation rate in the placebo arm, and R_{ED80} is the observed ovulation rate in the selected dose arm.

A flow diagram is presented in Figure 1 of Section 15.2.1 to illustrate the decision tree for the two-interim adaptive design. Further details, such as the criteria for efficacy success using the group sequential method, the Bayesian predictive probability of future success to determine futility, the

rationales behind the 20% threshold to drop low dose, the ED80 dose-selection rule and dose-response evaluations are described in Section 9.2.1.1. Simulation results to assess operating characteristics of the design are given in Section 15.2.

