9.2.1.1 Bayesian Adaptive Design Rules

This section provides details for the decision rules to be implemented in the Bayesian adaptive study design.

Success criterion using group sequential strategy

To account for the multiplicities introduced by early success interim analyses, Pocock boundaries are used. Thus, the success threshold at each analysis corresponds to a nominal p-value < 0.0131 to maintain an overall one-sided type I error rate of 0.025.

The simulation results in Figure 13 for Scenario 7 in Section 15.2.3, as well as the justification provided in Section 15.2.4, show that the type I error is well controlled under the null hypothesis using the success boundary.

Futility criterion

Given the data collected at each interim time point, we compute the Bayesian predictive probability that the primary analysis will meet the success threshold once all arms have n = 15 subjects. If the predictive probability is less than 0.05, then the trial will be declared as a failure and terminate at this point due to futility.

The Bayesian predictive probability is calculated in the following fashion. First, for each arm d, we determine the number of future subjects required to complete the study, m_d . Then, the number of future responders occurring in arm d, Z_d , is generated from a Beta-Binomial distribution:

$$(Z_d | n_d, x_d) \sim BetaBinomial(m_d, a + x_d, b + n_d - x_d),$$

where n_{d} , x_{d} are the numbers of subjects and responders in arm d observed at interim analysis, and a non-informative prior Beta distribution with parameters a = 0.5 and b = 0.5 is used independently for each arm.

A large number of predicted values are sampled from the Beta-Binomial distribution for each arm, resulting in 1000 "complete" datasets. The predictive probability of eventual trial success is then the proportion of these complete datasets for which the primary analysis success threshold is met (p-value < 0.0131).

Dropping the low dose

If the observed response rate for the low dose meets the condition in inequality (2), then low dose will be dropped from additional enrolment, should the trial need to continue with the high dose, middle dose and placebo to assess the primary efficacy endpoint at the next analysis timing.

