The remaining sample size that had been planned for the low dose will be reallocated among the remaining arms. Thus the sample size for the placebo, middle, and high doses may either be 9, 12, 15, 16, or 17 subjects, depending on whether early success is declared, and whether low dose is dropped at the first or second interim analysis.

The 20% threshold to drop low dose is chosen based on the ED80 dose-selection rule, as the maximum of the most effective treatment effect can reach 100% (with the success rate in the placebo group expected to be close to 0). It ensures that when the threshold is met, the low dose does not qualify as the ED80 dose. Furthermore, we present in Table 3 below the Bayesian predictive probabilities of selecting low dose as ED80, should it proceed to a later analysis, for a range of borderline interim analysis observations where the 20% threshold is just met. A non-informative prior Beta (0.5, 0.5) is used for all treatment arms and 10000 predictions were generated. The results show that such probabilities are small: <10% in all cases and <5% in all but three cases. Therefore, 20% is a justifiable choice for the threshold to drop low dose early.

Table 3 Bayesian Predicted Probability of Selecting Low Dose as ED80 at a Later Analysis when Low Dose was Dropped Early

		rxnary	ois when L	in Dust was	, Dropp	cu Larry
N per arm	N per arm	Observe	d n (%) of su	ccesses at	Diff*	Probability of
at interim	at later	interim analysis			(%)	selecting low dose as
analysis	analysis	High-dose	Mid-dose	Low-dose		ED80 if continue
						with low dose
9	12	6 (67.8)	4 (44.4)	3 (33.3)	-22.2	0.0207
		5 (55.6)	5 (55.6)	3 (33.3)	-22.2	0.0735
		5 (55.6)	4 (44.4)	2 (22.2)	-27.8	0.0059
		5 (55.6)	3 (33.3)	2 (22.2)	-22.2	0.0062
		4 (44.4)	4 (44.4)	2 (22.2)	-22.2	0.0159
	15	6 (67.8)	4 (44.4)	3 (33.3)	-22.2	0.0304
		5 (55.6)	5 (55.6)	3 (33.3)	-22.2	0.0672
		5 (55.6)	4 (44.4)	2 (22.2)	-27.8	0.0136
		5 (55.6)	3 (33.3)	2 (22.2)	-22.2	0.0201
		4 (44.4)	4 (44.4)	2 (22.2)	-22.2	0.0555
12	15	8 (75.0)	6 (50.0)	4 (33.3)	-25.0	0.0015
		7 (58.3)	6 (50.0)	4 (33.3)	-20.9	0.0231
		7 (58.3)	5 (41.7)	3 (25.0)	-25.0	0.0012
		7 (58.3)	4 (33.3)	3 (25.0)	-20.8	0.0014
		6 (50.0)	5 (41.7)	3 (25.0)	-20.8	0.0211
		6 (50.0)	4 (33.3)	2 (16.7)	-25.0	0.0011
		5 (41.7)	5 (41.7)	2 (16.7)	-25.0	0.0059
		5 (41.7)	4 (33.3)	2 (16.7)	-20.8	0.0173

Diff* is the difference in observed success rates between the low-dose group vs. the pooled high- and mid-dose groups

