Dose-response evaluation and dose-selection

For trials that meet the primary analysis success threshold, we will subsequently select the ED80 dose, the lowest effective dose satisfying inequality (2). The ED80 dose will be labeled as such in the primary efficacy analysis table.

• As noted earlier, when the primary efficacy success is already declared at an interim analysis, but the success rate in the low-dose arm is not sufficiently low compared to the combined low- and high-dose success rate, the trial will continue to enroll more patients in the three dose arms only. Although no additional patients will be randomized to placebo, the success rate estimated from the enrolled placebo patients will be used in inequality (2) to determine the ED80 for the study.

Date: 07 Dec 2017 E-Statistical Analysis Plan-21977; Ver. 1.0 Supersedes: None Page 23 of 59

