10.5.3 Ovarian Hyperstimulation Syndrome (OHSS)

The frequency and severity of ovarian hyperstimulation syndrome will be presented in by-patient listings and summary tables as for AEs.

Date: 07 Dec 2017 E-Statistical Analysis Plan-21977; Ver. 1.0 Supersedes: None Page 30 of 59

11 Interim analyses

Two interim analyses are planned after approximately 9 and 12 patients per arm complete the study. The details of the interim analysis strategy are described in Section 9.2.

An independent data monitoring committee consisting of two unblinded clinicians and one unblinded statistician will be set up to review the interim analysis study results and make recommendations for the direction of the study, in accordance with the adaptive design decision-making rules specified in Section 9.2.1. In addition, independent statistician and programmer will be identified to generate the data analysis output. Individuals involved in the first and second interim analysis of the study will not be involved in the conduct of the study afterwards; individual patient identification will not be released to anyone who is directly involved in the conduct of the study.

The interim analysis process, the measures used to protect the blind and the integrity of the study, the communication plan, and the confidentiality agreement will be described in a separate document.

Date: 07 Dec 2017 E-Statistical Analysis Plan-21977; Ver. 1.0 Supersedes: None Page 31 of 59

12 Deviations from protocol analysis

13 References

- [1] International Federation of Pharmaceutical Manufacturers and Associations. Medical Dictionary for Regulatory Activities (MedDRA). Version 10.1. Reston, Virginia, USA; 2008.
- [2] WHO Collaborating Center for International Drug Monitoring. WHO Drug Dictionary. July 2008 edition. Uppsala, Sweden; 2008.
- [3] SAS Institute Inc. SAS Version 9.1. Cary, NC, USA; 2002-2003.
- [5] Jung, S.H. Stratified Fisher's exact test and its sample size calculation. Biometrical J. 2014;56. doi: 10.1002/bimj.201300048.
- [6] van Elteren, P. H. (1960). "On the combination of independent two-sample tests of Wilcoxon," Bulletin of the International Statistical Institute, 37, 351-361.

14 Tables, Listings and Figures

The document with tables, figures and listings (TLF) shells will be presented in a separate document.

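### The SAP's operative drop rule for the low dose cites the wrong inequality, and after interim success the stop and continue rules use different comparators, so both can apply to the same data

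*SAP*

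**What the plan says.** **Two inequalities.** Inequality (1) requires R_low to lie at least 0.2 below R_(high+middle). SAP Section 9 defines these rates as "the observed ovulation rates in the low dose arm and the combined middle- and high-dose arms, respectively". Inequality (2) is the ED80 condition: the dose keeps at least 80% of the largest effect over placebo.

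**No interim success.** SAP Section 9, the protocol synopsis and Protocol 9.6.1 drop the low dose if (1) holds. SAP 9.2.1.1, for the same branch, says: "If the observed response rate for the low dose meets the condition in inequality (2), then low dose will be dropped from additional enrolment". Two paragraphs later it explains the 20% threshold: "It ensures that when the threshold is met, the low dose does not qualify as the ED80 dose".

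**Interim success.** The trial stops (outcome 4) if (1) holds, so the comparator is middle plus high. It continues without placebo (outcome 3) when, in SAP Section 9, "the response rate in the low-dose arm is within 20% from the combined low- and high-dose success rate". SAP 9.2.1.1 repeats this as "the success rate in the low-dose arm is not sufficiently low compared to the combined low- and high-dose success rate". The protocol synopsis and Protocol 9.6.1 also have "within 20% from the combined low- and high-dose success rate".

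**Who applies the rules.** Under SAP Section 11 the monitoring committee makes recommendations "in accordance with the adaptive design decision-making rules specified in Section 9.2.1". Under Protocol 9.9 it does so "in accordance with the adaptive design decision-making rules specified in Section 9.6".

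**The concern.** Inequality (2) identifies a low dose that works well enough to be selected. Read literally, SAP 9.2.1.1 drops the arm because it performs well and keeps it when it performs badly. That contradicts SAP Section 9, the protocol, and the purpose given in the same section. The SAP sends the committee to the section with the wrong citation, and the protocol sends it to one with the right citation.

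After success, stop and continue should be complements. With different comparators they overlap, and they also leave a small gap.

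These rules settle whether an arm keeps enrolling and whether the trial ends. A committee that has to pick between texts with unblinded data in hand is no longer following a prespecified rule.

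**Working it through.** **Inputs.** Success is one-sided p < 0.0131 for pooled middle plus high against placebo (SAP 9.2.1.1). The first look has 9 per arm. True rates are those of SAP 15.2.3, in the order placebo, low, middle, high. The checks use an unstratified Fisher test and equal arms, as the SAP's examples imply, and read 20% as percentage points. First-look results come from exact enumeration of all outcomes.

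**1. The plan's own figures.** The example p-values 0.0052 (10/18 v 0/9), 0.0197 (8/18 v 0/9) and 0.0139 (9/24 v 0/12) reproduce. So does the fixed-design type I error of 1.018×10⁻¹¹. With inequality (1) and middle plus high:

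| First look | Computed | SAP |
|---|---|---|
| Scenario 1, success | 93.4% | 93.3% |
| Scenarios 1/2/3, success and stop | 26.9/50.6/75.7% | 27.8/50.5/76.5% |
| Scenario 4, low dropped, trial continues | 46.6% before futility stops, 45.9% after | 46.2% |

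With low plus high as the comparator, success-and-stop would be 9.5/26.5/49.2%. The simulations therefore used (1) with middle plus high.

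**2. (1) and (2) exclude each other.** Let M be the best observed rate, P the placebo rate and L the low-dose rate. Inequality (2) gives L ≥ 0.8M + 0.2P. Inequality (1) gives L ≤ M − 0.2, because the middle-plus-high average cannot exceed M. Both need 0.8M + 0.2P ≤ M − 0.2, that is M − P ≥ 1. So M = 1, P = 0, and L = 0.8 exactly. A rate of 0.8 is impossible with 9 or 12 patients (7.2 or 9.6 responders).

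Example Trial 3 shows the conflict (low 2/9, middle 3/9, high 5/9, placebo 0):
- (1) holds: 0.222 ≤ 0.444 − 0.2 = 0.244.
- (2) fails: 0.222 < 0.8 × 0.556 = 0.444.

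The SAP drops the arm. Its 9.2.1.1 wording would keep it.

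**3. Size of the drop-rule error (first look, before futility stops).**

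| | No success | No success and (1) | No success and (2) |
|---|---|---|---|
| Scenario 1 (1/60/65/70%) | 6.6% | 0.35% | 5.1% |
| Scenario 4 (1/10/40/50%) | 61% | 46.6% | 1.4% |

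In Scenario 1 the low dose is strictly the best arm, yet dropped under (2), in 2.8% of all trials.

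**4. Overlap of stop and continue.** With equal arms, being within 20 points of low plus high means L ≥ (L + H)/2 − 0.2, that is L ≥ H − 0.4, where H is the high-dose rate. Writing Mid for the middle-dose rate, both rules apply when H − 0.4 ≤ L ≤ (Mid + H)/2 − 0.2.

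Example: placebo 0/9, low 4/9, middle 6/9, high 7/9, with p = 0.0004.
- Against middle plus high: 13/18 − 4/9 = 0.722 − 0.444 = 0.278, so stop.
- Against low plus high: 11/18 − 4/9 = 0.611 − 0.444 = 0.167, so continue.

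Both rules apply in 17.7%, 24.8%, 26.6%, 7.7%, 7.8% and 0.6% of all trials in Scenarios 1 to 6. A few successes meet neither rule. With placebo 0, low 4, middle 1, high 8 of 9, p = 0.0104; low is 0.056 below middle plus high and 0.222 below low plus high. This has probability 0.3% in Scenario 1.

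**5. Table 3 (secondary).** It prints 6/9 as 67.8% and 8/12 as 75.0%; both are 66.7%. Exact Beta-Binomial values from the stated Beta(0.5, 0.5) prior depend on two unstated inputs: the placebo count and whether trial success is required.

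| Placebo responders | Success required | Rows ≥ 5% | Maximum | Rows more than 3 simulation SE from print |
|---|---|---|---|---|
| 0 | no | 5 | 10.2% | 16 of 18 |
| 0 | yes | 4 | 9.6% | 11 of 18 |
| 1 | no | 3 | 8.4% | 10 of 18 |
| 1 | yes | 0 | 4.5% | 14 of 18 |

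The SAP prints three rows at or above 5%, maximum 7.35%. One row, with 0 placebo responders and success not required: high 4, middle 4, low 2, going from 9 to 12 per arm, gives 0.0655 against a printed 0.0159.

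**The case against.** The strongest reply is that the intent is recoverable. The paragraph after next in SAP 9.2.1.1 explains the 20% threshold, and the same section later uses (2) for dose selection. Example Trials 3 and 4 apply (1). Example Trial 2, a success-then-continue case, compares the low dose with the pooled middle and high arms. The committee's working process is in a separate document that may already be right. Every percentage for harm supposes that someone follows wording that was not meant. All of this is fair, and it makes these drafting errors rather than a flawed design. It does not remove the need to correct them: the section named in the SAP as governing the recommendation gives the wrong condition, and the wrong comparator stands in four places across both documents.

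Three refinements also stand:
- (2) is opposite in direction to (1) but not its exact complement. At 9 per arm, 1965 of 7975 outcomes (those with an active arm at or above placebo) meet neither.
- The Table 3 summary sentence fails with 0 placebo responders but matches the row count obtained with 1 responder and success not required. Only the failure of individual rows to reproduce is independent of that choice.
- The protocol has < in (1) and the SAP has ≤. This cannot matter at exactly 9 or 12 per arm. It can at 10, which is what the first 40 randomised patients give (15 at 1:1:1, then 25 at 1:2:1:1): low 3/10 against 10/20 is an exact tie.

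**Conclusion.** The concern holds. SAP 9.2.1.1 cites the wrong inequality for dropping the low dose, and the continue rule names the wrong comparator in the protocol synopsis, Protocol 9.6.1, SAP Section 9 and SAP 9.2.1.1. Both need correcting before the first look.

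If followed literally, the first error nearly removes low-dose dropping where the arm is weak (46.6% to 1.4% of trials in Scenario 4). It also drops the arm in 5.1% of trials, instead of 0.35%, where it works (Scenario 1). The second leaves the stop decision ambiguous in 17.7% to 26.6% of trials in Scenarios 1 to 3, and in under 8% in Scenarios 4 to 6.

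The SAP's power and type I error are unaffected provided (1) is what is applied. Under a literal (2), simulation of the full design gives power of about 0.890 instead of 0.915 in Scenario 4, 0.767 instead of 0.815 in Scenario 5, and 0.361 instead of 0.432 in Scenario 6.

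The figures assume an unstratified test, equal arms and absolute percentage points. The Table 3 point is minor and does not overturn the 20% threshold.

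**What to change.** - In SAP 9.2.1.1, paragraph on dropping the low dose, cite inequality (1) instead of (2).
- In the protocol synopsis, Protocol 9.6.1, SAP Section 9 and SAP 9.2.1.1, name the combined middle- and high-dose rate in the continue rule, so that outcome 3 is the complement of outcome 4.
- Recompute Table 3 from the Beta-Binomial model, state the placebo count and whether trial success is required, correct the two percentages, and restate the summary sentence to match.
- Use one sign in (1) in both documents.
- Optional: Example Trial 1 should read 10/18 − 1/9 = 0.556 − 0.111 = 0.444 (difference taken before rounding). In Scenario 1, replace the remark that the low dose is seldom dropped by the counts, at least 2782 + 570 = 3352 of 10,000.

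The cost is wording in two documents and a short recalculation of one table. No patients are added, and the simulated design is unchanged. The one downside is that the Table 3 support may look slightly less favourable, depending on the placebo count assumed.
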